5.2 Sample Size

5.2.1 Phase 1b Dose Determination Phase

Three to six patients will be enrolled in each dose cohort based on a standard Phase 1 dose-finding scheme.

A starting sample size of 3 evaluable patients per dose cohort, expanding to 6 in the event of a marginal DLT rate (33%) was deemed to be a safe and conventional approach in dose-finding. Assuming a true DLT rate of 5% or less, there would be a 3% chance that dose escalation would be halted in a given cohort (i.e. observing 2 or more patients with DLT). If a true DLT rate of 50% is assumed, then there would be an 83% chance that dose escalation would be halted in a given cohort.

6 patients will need to be treated in a dose level for it to be considered as MTD or RP2D.

**Statistical Analysis Plan
SNDX-275-0602 (TRIO025)
DM-025-037**

Patients who discontinued the study for reasons other than study drug related toxicities before completing Cycle 1 will be replaced.

Therefore, between 6 and 18 patients will be included in the Dose Determination Phase.

5.2.2 Phase 2 Expansion Phase

The following assumptions are made:

- Patients in the control arm have true median PFS of 4 months
- Patients in the experimental arm have true median PFS of 7 months (under exponential distribution, true PFS hazard ratio of 0.57)
- Expected accrual duration will be 9 months and an additional 9 months of follow-up. The α type I error rate is set to 10% (1-sided)
- The β type II error rate is set to 20% (i.e. the power of the trial will be 80%)

Under these assumptions, 70 patients (35 per arm) will be enrolled in the trial, which is projected to result in 60 PFS failures, defined as documented disease progression by RECIST 1.1 or death due to any cause without documented disease progression beforehand, within approximately 18 months of the first patient randomized.

It is anticipated that the number of patients that drop out without PFS failure will be low (2-3%). Depending on the actual number of such dropouts, the number of patients accrued maybe increased by 6-10 patients to accommodate for a higher-than-expected number of dropouts.

5.3 Randomization and Stratification

The randomization technique used for the study is a stochastic minimization, using minimization probability parameter of 0.80. The randomization is performed via ID-net (which is the IWRS from IDDI).

Prior to dosing, eligible patients are randomized in a 1:1 ratio into 2 treatment arms, stratified by geographic location.

5.4 Timing of Analyses

5.4.1 Phase 1b Dose Determination Phase

A safety analysis will be performed at the completion of the dose determination phase.

**Statistical Analysis Plan
SNDX-275-0602 (TRIO025)
DM-025-037**

5.4.2 Phase 2 Expansion Phase

The following analyses are planned:

- An interim safety analysis will be performed following the completion of Cycle 1 for the first 20 patients enrolled in the Phase 2 expansion phase, and will utilize a Data Safety Monitoring Board (DSMB).
- An interim efficacy analysis will be performed when 45 PFS events have observed. Data cut-off for the analysis will be based on the calendar date of the 45th PFS event (per RECSIT 1.1). Safety and secondary endpoints will also be evaluated. The same data cut-off used for the PFS analysis is also used for the corresponding analysis of safety and secondary endpoints.
- Primary efficacy analysis will be performed when 60 PFS events are observed. Similarly, the data cut-off for the primary analysis will be based on the calendar date of the 60th PFS event. Safety and secondary endpoints will coincide with the primary PFS analysis.
- End of study analysis for safety and OS analysis will be performed when the last patient terminates study treatment.

6. DEFINITIONS

6.1 Progression-Free Survival (PFS)

The duration of PFS, defined as the number of months from randomization to the earlier of progressive disease or death due to any cause. One month is considered 30.4375 days.

PFS (months) = (Date of Progression or Censoring – Date of Randomization + 1) ÷ 30.4375

Patients who meet one or more of the following conditions at the time of primary analysis will be censored:

- No screening or post-screening disease assessments unless death occurred prior to the first planned assessment.
- Initiation of a new anticancer therapy in the absence of documented progression.
- Death or progressive disease after missing 2 or more consecutively scheduled disease assessment visits
- Last known to be alive and progression-free on or before the data cut-off date

**Statistical Analysis Plan
SNDX-275-0602 (TRIO025)
DM-025-037**

The following table, adopted from FDA guidance “*Guidance for Industry Clinical Trial Endpoints for the Approval of Cancer Drugs and Biologics*” (May 2007) illustrates how the cases will be handled for primary analysis. If a patient is censored satisfying more than one criteria, the situation with the earliest date will be considered.

Table 1 – Primary Rules for Determining Date of Progression or Censor for Primary Progression-Free Survival

	Situation	Date of Progression or Censoring	Outcome
1	Death before first PD assessment	Date of death	Progressed
2	Death or disease progression between planned disease assessments	Date of death or first disease assessment showing disease progression, whichever occurs first	Progressed
3	No baseline tumor assessments	Date of randomization	Censored
4	New anticancer treatment started (in absence of documented progression)	Date of last radiological assessment of measured lesions prior to the start of the new anticancer treatment	Censored
5	Death or progression after more than 2 or more consecutive visits	Date of last radiological assessment of measured lesions without documented disease progression that is before the first missed visit	Censored
6	Last known to be alive and progression-free on or before the data cut-off date	Date of last radiological assessment of measured lesions	Censored

The following sensitivity analyses will also be provided:

Table 2 – Progression-Free Survival Sensitivity Analysis

**Statistical Analysis Plan
SNDX-275-0602 (TRIO025)
DM-025-037**

Analysis #	Definition and/or changes from primary analysis; unless otherwise stated, the same PFS censoring rules will be applied
1	Per-protocol analysis set, instead of full analysis set
2	PFS events occurring immediately after two or more missing visits will not be censored
3	Patients who discontinue treatment due to any reason other than disease progression or death are censored at the date of last tumor assessment prior to (or at) treatment discontinuation
4	Patients who received new anticancer treatment without documented progression will not be censored
5	Worst case analysis: A patient who is lost to follow-up (or withdrew consent from study participation) before documented progression will be considered progressed at first scheduled radiological assessment date after lost to follow-up (or withdrew consent) (i.e. last radiological assessment + 42 days)

All analyses described above will use the same methodologies as the primary analysis, except changes as noted in the second column. Each analysis will modify only the rule as stated in the specific row; i.e. rows will not be combined unless otherwise specified.

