A treatment cycle is 3 weeks (21 days) in length. The dose of atezolizumab will be fixed at 1200 mg IV q 3 weeks (day 1 of each cycle) for all patients. Entinostat (during the Phase 1b Dose Determination Phase) and entinostat / placebo (during Phase 2, Expansion Phase) will be administered orally on days 1, 8 and 15 of each 21 day cycle. The Dose Determination Phase will begin with a starting dose (dose level 1) of entinostat 5 mg po weekly. If dose level 1 exceeds the MTD, then entinostat 3 mg po weekly (dose level -1) will be investigated. If dose level -1 exceeds the MTD, then entinostat 2 mg po weekly (dose level -2) will be investigated. Dosing is planned to be continuous unless interrupted for management of an adverse event. The entinostat dose determined appropriate for combination with atezolizumab will then be taken forward into the Phase 2 Expansion Phase of the study as the RP2D.

During treatment, patients will attend study center visits and have study evaluations performed on C1D1, C1D8, and C1D15; D1 and D15 of C2; and on D1 of each cycle thereafter. Patients will have radiological disease assessments performed within 28 days prior to the first dose of study drug, and then every 6 weeks (+/- 3 days) through week 36 (Weeks 6, 12, 18, 24, 30, 36) until unequivocal progressive disease. Patients remaining on study after week 36 will undergo radiological disease assessments every 9 weeks (+/- 3 days) until unequivocal progressive disease occurs. Disease will be assessed by computed tomography (CT), magnetic resonance imaging (MRI), and bone scans, as appropriate using the same method as used for the screening evaluation, and response will be assessed by the Investigator using RECIST 1.1.

Safety will be assessed during the study by documentation of AEs using United States (US) National Cancer Institute (NCI) Common Terminology Criteria for Adverse Events (CTCAE), version 4.03, clinical laboratory tests, physical examinations, vital sign measurements, electrocardiograms (ECGs), and Eastern Cooperative Oncology Group (ECOG) performance status. Adverse events of special interest (AESI) will be collected and reviewed in a manner consistent with serious adverse event reporting procedures.

Fresh tumor tissue core biopsy samples will be collected during the study as follows:

- During screening from all patients on a mandatory basis. Archival biopsies when available will also be collected for comparison.

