10. STUDY TESTS AND OBSERVATIONS

After provision of written informed consent, patients will be screened for study eligibility within 21 days before study enrollment. Patients who are determined to be eligible based on screening assessments and who are enrolled, **must begin treatment (C1D1) with entinostat/placebo in combination with atezolizumab within 3 business days of the date of enrollment/randomization.**

A cycle is 21 days in length. Patients will attend study center visits and undergo study evaluations on C1D1, C1D8, and C1D15; D1 and D15 of C2; and on D1 of each cycle thereafter.

Patients will have radiological disease assessments during screening and then during treatment and follow-up every 6 weeks (+/-3 days) (Week 6, Week 12, etc.) through week 36 and then every 9 weeks (+/- 3 days) thereafter until unequivocal progressive disease. This schedule is to be followed both during study treatment and following discontinuation of study treatment in the absence of progressive disease.

After discontinuation of study treatment, patients will complete an EOT visit within 7 days (+/- 3 days) after the last study drug dose and a Safety Follow-up visit 30 days (+/- 3 days) thereafter. After completion of the 30-day Safety F/U visit, patients who have not experienced PD are to continue to undergo radiological assessments every 6 weeks through week 36 and then every 9 weeks thereafter until unequivocal progressive disease. The purpose of the post-treatment follow-up is to ascertain the duration of PFS for all patients in the study. After progressive disease, surviving patients are to be followed every 3-months for documentation of subsequent therapy and survival until closure of the study or death.

Protocol-required tests, observations, and procedures are summarized in [Table 1-1](#).

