10.3.1 Tumor Measurements and Disease Response Assessment

10.3.1.1 Tumor Measurement and Assessment

Initial tumor imaging at screening must be performed within 28 days prior to initial study drug dosing (C1D1). (Scans performed as part of routine clinical management are acceptable for use as initial tumor imaging if they are of diagnostic quality and performed within 28 days prior to C1D1 and can be assessed by the central imaging vendor.) Patients will have radiological disease assessments performed every 6 weeks (+/-3 days) (Week 6, Week 12, etc.) during study treatment through week 36 or until progressive disease. If progressive disease has not

occurred by week 36, radiological assessments will be then be done every 9 weeks (+/-3 days) until progressive disease. If a patient comes off study for reasons other than progressive disease, radiological assessments will continue on this same study schedule until progressive disease is unequivocally documented. Images should be kept to the calendar schedule and not be delayed for delays in cycles or study drug administration. Disease response in target and non-target lesions will be assessed locally by the Investigator using RECIST 1.1 and irRECIST.

Measurable Disease

To be eligible for study participation, all patients must have documented measurable disease per RECIST 1.1 that has been radiologically documented within 28 days prior to initiating study drug treatment, defined as follows:

At least 1 measurable lesion:

- ≥ 10 mm in longest diameter on an axial image by CT scan or MRI with ≤ 5 mm reconstruction interval
 - If slice thickness is greater than 5 mm, longest diameter must be at least 2 times the thickness
- ≥ 20 mm longest diameter by chest X-ray (if clearly defined and surrounded by aerated lung); CT is preferred, even without contrast.
- Lymph nodes ≥ 15 mm in short axis on CT scan (CT slice thickness of ≤ 5 mm)

If there is only 1 measurable lesion and it is located in previously irradiated field, it must have demonstrated progression according to RECIST 1.1.

Non-measurable Lesions

Non-measurable lesions are defined per RECIST 1.1 as the following and should be captured and followed accordingly and within the eCRF according the eCRF guidelines.

- Masses < 10 mm
- Lymph nodes ≥ 10 to < 15 mm in short axis
- Leptomeningeal disease
- Ascites, pleural or pericardial effusion
- Inflammatory breast disease (cont'd on next page)
- Lymphangitic involvement of skin or lung

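### The 'worst case' PFS sensitivity analysis contradicts its own dating rule for last scans from week 36 on, and its label promises more than it gives; the effect is small

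*SAP*

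**What the plan says.** SAP section 6.1, Table 2, analysis 5 (labelled a worst case) covers "A patient who is lost to follow-up (or withdrew consent from study participation) before documented progression". No arm is named, so it applies to both. Such a patient "will be considered progressed at first scheduled radiological assessment date after lost to follow-up" or withdrawal, and the row puts a number on that date: "i.e. last radiological assessment + 42 days". The note under the table adds that "All analyses described above will use the same methodologies as the primary analysis", apart from the change named in each row, so analysis 5 feeds the same two-arm stratified log-rank test and Cox model. Each row alters only its own rule.

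Protocol section 10 sets scans "every 6 weeks (+/-3 days) (Week 6, Week 12, etc.) through week 36 and then every 9 weeks (+/- 3 days) thereafter" and applies this schedule both during study treatment and after it stops. The synopsis and sections 6.1, 9.9 and 10.3.1.1 agree. Section 10.3.1.3 has the 9-week switch for patients on treatment, but for patients who stop therapy without documented progression it gives 6-weekly imaging with no switch. Section 10.3.1.1 allows the screening scan up to 28 days before C1D1.

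SAP 5.2.2 and Protocol 13.1.2 expect 2-3% dropout without PFS failure. The protocol synopsis promises alternative censoring conventions to address, among other things, dropouts whose progression was not documented. Analysis 5 is the only row of Table 2 that counts lost or withdrawn patients as progressed.

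**The concern.** The words of the rule and the number that explains them give different dates for some patients. Two programmers could follow the same row and produce different event times: one using the next scan on the schedule, the other adding 42 days throughout.

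The label is a separate matter. The row's output is a hazard ratio and a test between arms, so a reader may take 'worst case' as a limit on how far dropout could weaken the treatment effect. Imputing events in both arms does not give that limit in general.

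**Working it through.** **Where 42 days is right.** 6 weeks x 7 = 42 days. This reproduces the SAP figure for last scans at weeks 6, 12, 18, 24 and 30.

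**Where it is not.**
- Last scan at week 36 or later: the next scan is 9 x 7 = 63 days on (36 to 45, 45 to 54, and so on). The bracket is 63 - 42 = 21 days early, or 21 / 30.4375 = 0.69 month.
- Screening scan only: at the limit of the window, -28 + 42 = day 14 from C1D1. The first scheduled scan is week 6 (day 42), so the bracket is up to 42 - 14 = 28 days early, if analysis 5 applies to such patients at all.
- Scan missed before loss. Illustration: last scan week 12 (day 84), week 18 (day 126) missed, lost on day 140. The bracket gives 84 + 42 = day 126, before the loss. The words require a date after it, here week 24 (day 168).

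**Who reaches week 36.** Week 36 is 252 / 30.4375 = 8.28 months. Under the design medians, 2^(-8.28/4) = 0.238 of control and 2^(-8.28/7) = 0.441 of entinostat patients are event-free then, or 8.3 and 15.4 of 35. These are patients at risk of later misdating, not misdated patients; only those subsequently lost or withdrawn count.

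**Effect on the comparison.** Simulation of 1,500 trials: 70 patients 1:1, exponential PFS with medians of 4 and 7 months, 9 months' accrual plus 9 months' follow-up, progression detected at protocol scans, unstratified log-rank at one-sided 0.1, no interim adjustment. The baseline scan was placed at day 0 and no scans were missed, so the redating effect covers the week-36 error only. The 3% rate is the top of the documents' range; 10% and 15% are assumptions.

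| Dropout | Mean patients imputed | Of these, last scan at week 36 or later | Mean absolute change in HR from redating |
|---|---|---|---|
| 3% | 1.93 | 0.39 | 0.002 |
| 10% | 6.60 | 1.21 | 0.005 |
| 15% | 10.22 | 1.81 | 0.007 |

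Median hazard ratio, with rejection rate in brackets:

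| Dropout | Both arms, +42 days (SAP) | Both arms, scheduled date | Entinostat only, scheduled date |
|---|---|---|---|
| 3% | 0.549 (76.3%) | 0.549 (76.5%) | 0.562 (73.5%) |
| 10% | 0.564 (73.3%) | 0.559 (73.3%) | 0.613 (62.1%) |
| 15% | 0.594 (69.1%) | 0.589 (69.2%) | 0.688 (47.3%) |

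The simulation error of a single rejection rate near 75% is sqrt(0.75 x 0.25 / 1,500) = 1.1 percentage points. Dropout was simulated at the same rate in both arms. Redating hardly matters; the choice of arm matters as dropout rises.

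**The case against.** The strongest reply is that this is one of five sensitivity analyses, does not touch the primary test, and at the planned dropout concerns a fraction of one patient. That stands and sets the severity.

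Second, the SAP never says for whom the case is worst. Counting every dropout as progressed is worst case for each arm's absolute PFS, and nowhere does the SAP claim that analysis 5 bounds the treatment effect. That also stands: this half concerns the label and the choice of analysis, and is not a contradiction.

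Third, Protocol 10.3.1.3 supports 42 days for patients already off therapy. It does, but it conflicts with sections 6.1, 9.9, 10 and 10.3.1.1, and the bracket also covers patients lost while on treatment.

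Fourth, SAP 6.1 separately censors patients with no screening or post-screening assessments, and each row changes only its own rule, so patients with only a screening scan may stay censored. The text does not settle this, so the 28-day figure is conditional as well as a maximum.

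Three stronger readings are tempting and are not supported:
- *The row would look reassuring if losses were concentrated in the entinostat arm.* The reverse is true. If all losses are in that arm, analysis 5 and entinostat-only imputation, on the same dates, give the same data set. They differ only through control-arm losses.
- *About 24 of 70 patients would be misdated.* That is the number event-free at week 36 (8.3 + 15.4), which is the wrong denominator.
- *The early dating flatters entinostat.* More entinostat than control patients pass week 36, so early events tend to count slightly against it: 0.564 against 0.559 at 10% dropout.

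**Conclusion.** The bracket is wrong as written for last scans from week 36 on, by 21 days, and can fail the row's own wording in the two narrower situations shown above. About 80% of simulated dropouts had an earlier last scan (1 - 0.39/1.93), where 42 days agrees with the schedule. The hazard-ratio shift of about 0.002 at 3% dropout rests on the design's exponential medians and on complete scanning up to loss; screening-only and missed-scan patients would add to it by an amount not calculated here.

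The row is not the least favourable treatment comparison when losses are balanced or mainly in control. At 3% dropout the gap is 0.549 against 0.562. It widens to 0.589 against 0.688 (both on scheduled dates) only at an assumed 15%. The documents give no such rate, although they allow 6-10 extra patients for higher dropout, which is 6/70 = 9% to 10/70 = 14% of the planned number. Severity: minor.

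**What to change.** 1. Replace the bracket in analysis 5 with: *the next protocol-scheduled assessment after the date of loss or withdrawal (6-weekly through week 36, 9-weekly after), counted from C1D1, or from randomization if never treated*. The last clause is needed because the Full Analysis Set includes randomized patients who were never dosed. State whether patients with no post-baseline scan are imputed or stay censored.
2. Reconcile Protocol 10.3.1.3 with sections 6.1, 9.9 and 10 on imaging after treatment stops.
3. Rename the row, for example *dropouts counted as progressed, both arms*.
4. Optionally, add a row that counts losses as events in the entinostat arm only and censors them in control.

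The cost is SAP wording, a protocol clarification and a few lines of code, best settled before unblinding. The primary analysis and sample size do not change. The downside of item 4 is one more sensitivity analysis and a less favourable figure to report.

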6.2 Objective Response Rate (ORR)

ORR is defined as the crude proportion of patients achieving a best overall response of CR or PR assessed using RECIST 1.1. The best overall response assessed using irRECIST will also be analyzed separately and the corresponding ORR will be calculated. The overall response will be determined locally by the investigator at each scheduled assessment.

Per protocol (Section 10.3.1.3), partial or complete response should be confirmed by a repeat tumor imaging assessment not less than 4 weeks from the date the response was first documented.

The following table will be followed to assign a best overall response based on the achievement and confirmation of two consecutive assessments according to RECIST 1.1:

Overall response First time point	Overall response Subsequent time point (at Least 4 Weeks Later)	Best Overall Response
CR	CR	CR

**Statistical Analysis Plan
SNDX-275-0602 (TRIO025)
DM-025-037**

Overall response First time point	Overall response Subsequent time point (at Least 4 Weeks Later)	Best Overall Response
CR	PR	PR
CR	SD	SD
CR	PD	PD
CR	NE	SD
PR	CR	PR
PR	PR	PR
PR	SD	SD
PR	PD	PD
PR	NE	SD

$$ORR_{RECIST1.1} = \frac{\# \text{ of patients with best overall response as CR or PR}}{\text{Total number of patients}}$$

Similarly, irCR or irPR based on irRECIST will also be confirmed.

The following table is therefore used for best overall response based on irRECIST:

Overall response First time point	Overall response Subsequent time point (at Least 4 Weeks Later)	Best Overall Response
irCR	irCR	irCR
irCR	irPR	irPR
irCR	irSD	irSD
irCR	irPD	irPD
irCR	irNE	irSD
irPR	irCR	irPR
irPR	irPR	irPR
irPR	irSD	irSD
irPR	irPD	irPD
irPR	irNE	irSD

And ORR based on irRECIST is calculated as follows:

$$ORR_{irRECIST} = \frac{\# \text{ of patients with best overall response as irCR or irPR}}{\text{Total number of patients}}$$

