10.3.1.3 Disease Response Assessment Criteria

Patients will have radiological disease assessments performed every 6 weeks (+/-3 days) (Week 6, Week 12, etc.) during study treatment through week 36 or until unequivocal progressive disease. If progressive disease has not occurred by week 36, radiological assessments will be then be done every 9 weeks (+/-3 days) until unequivocal progressive disease. Images should be kept to the calendar schedule and not be delayed for missed study drug administration.

Partial or complete response should be confirmed by a repeat tumor imaging assessment not less than 4 weeks from the date the response was first documented. The tumor imaging for confirmation of response may be performed at the earliest 4 weeks after the first indication of response, or at the next scheduled scan if on a 6 week schedule, whichever is clinically indicated.

In subjects who discontinue study therapy without documented unequivocal progressive disease, every effort should be made to continue monitoring their disease status by tumor imaging every 6 weeks until (1) unequivocal progressive disease (2) death, or (3) the end of the study, whichever occurs first. All scans will be submitted (electronically whenever possible) to a central core radiologic laboratory within 3 days of being performed, where they will immediately be reviewed for readability. The lab will contact the site should any issues or questions arise.

Disease progression is determined locally, not by the central core radiologic lab. Scans from patients who were determined by the Investigator to have a response to treatment (CR or PR) will be reviewed by the core radiologic laboratory to confirm response. The lab will collect and hold all scans should the sponsor decide to have them read to confirm PFS outcomes.

Scans from non-responders may also be reviewed by the core radiologic laboratory at the direction of the Sponsor.

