6.3 Clinical Benefit Rate (CBR)

CBR is estimated based on the crude proportion of patients in each treatment arm whose best overall response during the course of study treatment is CR, PR or SD lasting for at least 24 weeks (measured from the date of randomization to the last date where SD is reported).

$$CBR_{RECIST\ 1.1} = \frac{\# \text{ of patients with best confirmed overall response as CR/PR/ SD lasting for} \geq 24 \text{ weeks}}{\text{Total number of patients}}$$

Similarly, CBR is calculated based on irRECIST as below:

$$CBR_{irRECIST} = \frac{\# \text{ of patients with best confirmed overall response as irCR/irPR/irSD lasting for} \geq 24 \text{ weeks}}{\text{Total number of patients}}$$

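### Two rules in the SAP 6.2 best-response table can misclassify patients: response-then-PD scored as PD (affects CBR for late responders only) and confirmation limited to consecutive scans (affects ORR and the endpoints built on it)

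*SAP*

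**What the plan says.** SAP 6.2 has two tables of the same form, one for RECIST 1.1 and one for irRECIST. The first is to "assign a best overall response based on the achievement and confirmation of two consecutive assessments according to RECIST 1.1". Its second column is headed "Subsequent time point (at Least 4 Weeks Later"). Every row starts with CR or PR. A response followed by PD returns PD; a response followed by SD or NE returns SD. The irRECIST rows run in parallel, including "irPR irPD irPD". No row starts with SD, no minimum duration is set for SD, and nothing says how several pairs in one patient are combined.

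Just above the table, the SAP says a response should be "confirmed by a repeat tumor imaging assessment not less than 4 weeks from the date the response was first documented". Protocol 10.3.1.3 has the same rule and adds that the confirming scan may be taken at 4 weeks at the earliest, "or at the next scheduled scan if on a 6 week schedule, whichever is clinically indicated".

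SAP 6.3 counts in CBR the patients "whose best overall response during the course of study treatment is CR, PR or SD lasting for at least 24 weeks", timing SD from randomization to the last visit reported as SD. Protocol 13.5.5 times SD from treatment start to first PD. SAP 6.5 and 6.6 restrict DOR and TTR to confirmed responders. Under protocol 10.3.2, an irPD that repeat imaging does not show is not confirmed. Scans are "every 6 weeks (+/- 3 days) through week 36 (Weeks 6, 12, 18, 24, 30, 36"), then every 9 weeks.

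**The concern.** The PD rows make no reference to what came before the response. A patient who has been stable for months, responds once and then progresses receives PD as her best response, and drops out of CBR. A patient who stays stable over the same period and progresses at the same visit is counted. More shrinkage earns a worse score. The table is also uneven within itself: the same unconfirmed response followed by a scan that could not be evaluated earns SD.

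The word consecutive sets a second condition that the 4-week rule does not contain. One unevaluable scan between two responses can cost the patient her responder status.

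Protocol 13.5.5 tests ORR between arms at one-sided 0.1 and analyses CBR by the same methods. An open or uneven rule lets two programmers obtain different rates from the same data, and settling it after unblinding would be a post hoc choice.

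**Working it through.** The documents give no expected rate, power or target for ORR or CBR, so there is no stated figure to reproduce. The check traces scan sequences through the table. Scan weeks are nominal.

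**1. PD row and ORR.** A response followed at once by PD is unconfirmed. The patient is a non-responder whether her best response is called SD or PD. All patterns of PR, SD and NE at weeks 6 to 36, ending in PD or reaching week 36, were enumerated (CR behaves like PR here): (1 + 3 + 9 + 27 + 81 + 243) + 3^6 = 364 + 729 = 1,093. Rescoring the PD row changed ORR in 0 of them.

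**2. PD row and CBR.** Take SD at every scan, a first PR, then PD at the next scan. Read literally, the table gives PD and CBR fails in every line below. If the best response were SD instead, CBR would pass where the duration reaches 24 weeks (bold).

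| First PR | PD | Last reported SD (SAP 6.3) | PR visit counted as SD | To first PD (protocol 13.5.5) |
|---|---|---|---|---|
| wk 6 | wk 12 | 0 | 6 | 12 |
| wk 12 | wk 18 | 6 | 12 | 18 |
| wk 18 | wk 24 | 12 | 18 | **24** |
| wk 24 | wk 30 | 18 | **24** | **30** |
| wk 30 | wk 36 | **24** | **30** | **36** |

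In the last line, the patient with SD through week 24, PR at week 30 and PD at week 36 fails CBR. With SD at week 30 instead, her last SD is at week 30 and she passes. With NE at week 36 instead of PD, she scores SD with last SD at week 24 and passes.

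Across the 1,093 patterns, rescoring the PD row changes CBR in 8, 24 and 28 under the three clocks, left to right. If an earlier SD is credited as best response, the loss falls to 0, 2 and 3. These are counts of patterns, not of patients.

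**3. Consecutive rule.** Take PR at week 6, NE at week 12, PR at week 18, PD at week 24.
- The two responses are 18 - 6 = 12 weeks apart, so the 4-week rule is met.
- In the table, PR then NE gives SD and PR then PD gives PD. No consecutive pair confirms, so she is a non-responder and is left out of DOR and TTR.
- As a confirmed PR she would count in CBR. Scored SD on the SAP clock, she has no visit reported as SD and fails. Counting PR visits as SD gives 18 weeks, and she still fails. Only on the protocol clock does she reach 24 weeks and pass.
- PR-SD-PR-PD is lost from ORR in the same way. PR-NE-PR-PR and PR-SD-PR-PR-PD are already PR, because a later consecutive pair confirms.

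**4. irRECIST.** For irPR, irPD, irPR, the first pair returns irPD. Under protocol 10.3.2 that irPD was not shown on repeat imaging and so was not confirmed. The SAP table has no confirmation step for irPD.

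**5. Size.** With 35 patients per arm: 1/35 = 2.9 points, 2/35 = 5.7, 3/35 = 8.6. How many patients would be affected is an assumption in every case.

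**The case against.** The best counter-argument is that the table only resolves one response and its confirming scan. With no row starting with SD and no rule for combining pairs, it cannot be a complete per-patient algorithm. If best response is then taken across visits, the stable patient with a late PR keeps SD, and the CBR loss largely disappears. This stands as a possible reading, but the table neither allows nor forbids it, and it is the rule the SAP says will be followed. It also does nothing for the consecutive-scan problem.

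On confirmation, the protocol itself names the next scheduled scan as a usual time, and the column heading says subsequent, not next. Confirmation at the next scan is therefore not a plain breach of the protocol. What stands is narrower: consecutive is stricter than the 4-week sentence beside it, and the protocol's wording on timing is permissive.

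A reader might infer more than the documents support:
- That the PD row understates ORR. It cannot.
- That unconfirmed responders who progress are generally lost from CBR. With a first PR at week 6 or 12 and PD at the next scan, the patient fails the 24-week criterion under any scoring.
- That the loss falls more on the entinostat arm because it falls on patients with shrinkage. The documents give no frequency of these patterns in either arm, so no direction is shown.
- That the rows depart from published RECIST 1.1. The documents do not reproduce its best-response table, so this cannot be judged from them.

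**Conclusion.** The point holds in limited form. Read as written, the PD row gives a perverse CBR result for late first responses with PD at the next scan: from week 30 on the SAP clock, week 24 if the response visit counts as SD, or week 18 on the protocol clock. It has no effect on ORR. The consecutive condition removes from ORR, DOR and TTR those patients whose responses are split by NE or SD and never fall at two scans in a row. It also removes such patients from CBR where their SD duration falls short, as in the PR-NE-PR-PD example on the SAP clock. The irRECIST table carries both faults and also conflicts with protocol 10.3.2 on unconfirmed irPD.

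Each affected patient moves an arm's rate by 2.9 points, assuming 35 per arm. How many there would be is unknown. ORR, CBR, DOR and TTR are secondary endpoints; the primary PFS analysis and the sample size do not use best response and are unaffected. The change should be made because the rule is stated, its result is uneven, and the correction is cheap.

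**What to change.** Before unblinding, amend SAP 6.2 and 6.3:

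- Derive best overall response as the best status over all assessments up to PD; for irRECIST, up to confirmed irPD, consistent with protocol 10.3.2.
- Score an unconfirmed CR or PR as SD for that visit, including when PD follows, so that best response is PD only if no earlier assessment was SD or better.
- Accept a later CR or PR at least 4 weeks after the first as confirmation when only an NE scan lies between. State how an intervening SD is handled and, for irRECIST, an intervening unconfirmed irPD.
- Use one SD-duration clock for CBR, reconciling SAP 6.3 with protocol 13.5.5, and count an unconfirmed-response visit as SD. Rescoring the PD row alone would leave a patient with last SD at week 18 and PR at week 24 outside CBR on the SAP clock.

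The cost is SAP wording and derivation code, with protocol 13.5.5 aligned if its clock is the one changed. No new scans or data are needed.
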